8.7 Study size

No sample size has been calculated for this study. Based on the preliminary feasibility assessment, expected number of subjects to be involved in each data source would be approximately between 600 and 7900.

The feasibility count for each database is as follows: FinOMOP-HILMO (as of 2024-Nov): 2500; IPCI (as of 2024-Nov): 700; IQVIA-DA (as of 2024-Nov): 7900; NLHR (as of 2024-Jul): 2600; VID (as of 2024-Nov): 600

8.8 Analysis

Analyses will be conducted separately for each database. Before study initiation, test runs of the analytics will be performed on a subset of the data sources or on a simulated set of patients and quality control checks will be performed. Once all the tests are passed, the final package will be released in the version-controlled Study Repository for execution against all the participating data sources.

The data partners locally execute the analytics against the OMOP-CDM in R Studio and review and approve the by default aggregated results before returning them to the Coordination Centre. Sometimes multiple execution iterations are performed, and additional fine tuning of the code base is needed. A service desk will be available during the study execution for support.

The study results of all data sources are checked after which they are made available to the team in the Digital Research Environment and the Dissemination Phase can start. All results are locked and timestamped for reproducibility and transparency.

To prevent confidentiality issues, cell counts lower than 5 will be reported as "<5".

Details on type of analysis is given in Table 6.

Table 6. Description of study types and type of analysis.

Study type	Study classification	Type of analysis
Population Level DUS	Off-the-shelf	- Population-based incidence rates
Patient Level DUS	Off-the-shelf	 Characterisation of patient-level features Frequency and % of indication/s Estimation of minimum, p25, median, p75, and maximum treatment duration

8.8.1 Statistical model specification

The R package 'IncidencePravalence' (https://darwin-eu.github.io/IncidencePrevalence/) will be used to derive the incidence of JAKi use in the population level DUS, while R package 'CohortCharacteristics' (https://darwin-eu.github.io/CohortCharacteristics/) will be used for the patient characterisation and 'DrugUtilisation' (https://darwin-eu.github.io/DrugUtilisation/) for treatment characterisation in the patient level DUS.

8.8.2 Methods to derive parameters of interest

Incidence of new JAKi use

Incidence of new JAKi use (measured as prescription or dispensation), overall and for each individual JAKi ingredient, will be calculated annually as the number of individuals with a first JAKi prescription/dispensation per 100,000 per-years of the population at risk of getting exposed during the period for each calendar year. Those study participants who enter the denominator population will then contribute time at risk up to their first use during the study period or if they do not have a drug exposure, they will contribute time at risk up as described above in section 8.4 (Follow-up). Incidence rates will be given together with 95% Poisson exact confidence intervals. Illustration of the calculation of incidence use of the medicines of interest is shown below in Figure 3.

[figure not shown]

Figure 3. Illustration of the calculation of incidence on use of medicines of interest.

Example of incidence calculation is shown in **Figure 3**. Individuals (ID 1, 2) with sufficient data visibility will be included in the incidence calculation contributing to the time at risk (denominator). Individuals will be continued to contribute the time at risk until initiation of drug of interest (ID 1) or the end of follow-up for yearly cohort (ID 2). For individuals with exposure to JAKi before the start of the yearly cohort (ID 3) or with exposure at the start of the yearly cohort (ID 4), these subjects will not be included for the annual incidence calculation. Individuals will contribute time at risk only when they have with sufficient data visibility. Therefore, as illustrated by ID 5 and 6, individuals are only included and contribute to the denominator from the point with at least 365 days of data visibility.

For the incidence of each individual JAKi ingredient, only use of the specific individual JAKi ingredient will be considered. These subjects with previous exposure of other JAKi will be allowed to be included in the denominator during the calculation of population-level incidence. Each analysis on individual JAKi ingredient will be independent of other JAKi exposure. In another words, patients with exposure to different JAKi will be counted multiple times in different analyses.

Patient Characteristics

JAKi initiators will be characterized in terms of age, sex, and time from first diagnosis of prespecified indication to first JAKi exposure. Treatment characterisation will include indication and duration of treatment. Reporting on patient-level characterisation will be stratified by each individual JAKi ingredient and indication.

Duration of treatment

P3-C1-001 Stud	dy Protocol
----------------	-------------

Version: V3.0

Dissemination level: Public

Drug eras will be defined as follows: exposure starts at date of the first prescription, e.g., the index date the person entered the cohort. For each prescription, the estimated duration of use will be retrieved from the drug exposure table in the CDM, using the start and end date of the exposure. Subsequent prescriptions will be combined into continuous exposed episodes (drug eras) if the distance in days between end of the first exposure and start of the second exposure is ≤ 90 days. For the included individuals, the duration of JAKi use will be calculated by sum of duration of first drug eras during the study period. Treatment duration will be summarised providing the minimum, p25, median, p75, and maximum duration.

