7. RESEARCH QUESTION AND OBJECTIVES

Table 1. Primary and secondary research questions and objective.

A. Objective 1. Population-level drug utilisation

Objective 1:	To estimate the incidence of new JAKi use, overall and for each individual JAKi ingredient	
Hypothesis:	Not applicable	
Population (mention key inclusion- exclusion criteria):	The study includes all people available in the databases with at least 365 days of data visibility.	
Exposure:	Not applicable	
Comparator:	Not applicable	
Outcome:	JAKi (abrocitinib, filgotinib, baricitinib, upadacitinib, tofacitinib)	
Time (when follow up begins and ends):	From 1 st January 2017 until the most recent data lock for each included database.	
Setting:	Data will be collected from primary care and secondary care outpatient setting with the following databases:	
	- FinOMOP-HILMO (primary care, secondary care outpatient)	
	- IPCI (primary care)	
	- IQVIA DA Germany (primary care)	
	- NLHR (primary care, secondary care outpatient)	
	- VID (primary care, secondary care outpatient)	
Main measure of effect:	Annual incidence rates of JAKi use, for the entire class pooled together and for each JAKi ingredient	

B. Objectives 2. Patient-level characterisation and drug utilisation studies

Objective 2:	To characterise new JAKi users and treatment, overall and stratified by ingredient and indication	
Hypothesis:	Not applicable	
Population (mention key inclusion- exclusion criteria):	The study includes all patients available in the databases initiating JAKi therapy, with at least 365 days of data visibility before therapy initiation	
Exposure:	JAKi (abrocitinib, filgotinib, baricitinib, upadacitinib, tofacitinib)	
Comparator:	Not available	
Outcome:	Not available	
Time (when follow up begins and ends):	For treatment characterisation: from each JAKi therapy initiation until the discontinuation of index drug	
Setting:	Data will be collected from primary care and secondary care outpatient setting with the following databases: - FinOMOP-HILMO (primary care, secondary care outpatient)	

DARWIN M	P3-C1-001 Study Protocol	
○EU/V	Author(s): [name], [name]	Version: V3.0
,		Dissemination level: Public

	 IPCI (primary care) IQVIA DA Germany (primary care) NLHR (primary care, secondary care outpatient) VID (primary care, secondary care outpatient)

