8.3 Study period

The study period starts from 1st January 2017 until the most recent data lock for each included database (see **Table 3**).

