8.4 Follow-up

For the population-level drug utilisation study (objective 1), eligible study participants will begin to contribute person time from the latest of the following: (1) study start date, (2) date at which the observation period starts (i.e. 1st January of each year), or (3) date with at least 365 days of data visibility. Respective study participants will stop contribute person time at the earliest date of the following: (1) date on which the observation period ends (i.e. 31st December of each year), (2) end of data availability, or (3) date of first JAKi exposure if applicable (outcome of the incidence analysis).

For patient-level characterisation (objectives 2), eligible study participants with at least 365 days of data visibility will be follow-up from the date of first JAKi exposure until the earliest of (1) end of index JAKi treatment exposure, (2) death, (3) loss to follow-up, or (4) end of data availability.

[figure not shown]

Figure 1. HARPER diagram for index date definition in population level DUS (Objective 1).

- (a) Exposure of interest: any JAKi, individual JAKi ingredient
- (b) Earliest of: 31st December of each year, loss of follow-up, end of data availability, initiation of exposure of interest

Cohort Entry Date First exposure of interesta Day 0 **Washout Window** (No exposure of interesta) Days [- ∞, -1] **Data Visibility** Days [-365, -1] **Covariate Assessment Window** (Age, sex) Days [0, 0] **Covariate Assessment Window** (Indication) Days [-∞, -1] mmmmmFollow up Window Days [0, censor^b]

Figure 2. HARPER diagram for index date definition in patient level characterization (Objective 2).

- (a) Exposure of interest: individual JAKi ingredient
- (b) Earliest of: end of treatment with index exposure of interest, death, loss to follow-up, end of data availability

Time

P3-0	1-00	11 Sti	ıdv Pr	otocol

Version: V3.0

Dissemination level: Public

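### Treatment duration is summarised as raw quantiles of first eras that data lock and loss to follow-up cut short, so it understates time to discontinuation, most where the observable window is shortest (VID).

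*Protocol*

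**What the plan says.** - **Quantity.** Table 1 (section 7) gives the time frame for treatment characterisation as "from each JAKi therapy initiation until the discontinuation of index drug", and names treatment duration in months as the treatment measure for Objective 2.
- **Follow-up.** Section 8.4 ends Objective 2 follow-up at the earliest of (1) "end of index JAKi treatment exposure, (2) death, (3) loss to follow-up, or (4) end of data availability".
- **Variable.** In section 8.8.2, "the duration of JAKi use will be calculated by sum of duration of first drug eras during the study period". Prescriptions are joined into one era "if the distance in days between end of the first exposure and start of the second exposure is ≤ 90 days".
- **Statistic.** Section 8.8.2: "Treatment duration will be summarised providing the minimum, p25, median, p75, and maximum duration". Table 6 in section 8.8 has "Estimation of minimum, p25, median, p75, and maximum treatment duration", and the abstract lists the same five values.
- **Window.** Section 8.3: "The study period starts from 1st January 2017 until the most recent data lock for each included database". The locks in Table 3 run from 2022-01-01 (VID) to 2024-06-30 (NLHR).

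The protocol does not treat an era still running at data lock or loss to follow-up as incomplete, count such eras, or require a minimum follow-up. Section 11 makes only a general remark that duration rests on assumptions. It does describe an end-of-data artefact in IQVIA DA Germany, but for the incidence denominator, not for duration.

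**The concern.** A patient still on treatment at data lock enters the quantiles as if treatment had stopped that day. The 90-day joining rule adds to this: an era that ends fewer than 90 days before observation ends could still have been continued, so its end is unconfirmed.

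The purpose of the study (section 6) is to inform the feasibility of later safety studies, in a field where short follow-up is the stated problem. Results are given by ingredient, by indication and by database, so readers will see these medians side by side. Two strata with the same persistence but different observable windows would show different medians, and the shorter one could be mistaken for earlier stopping.

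**Working it through.** The protocol gives no expected duration, so there is no planned figure to reproduce. The check has four steps.

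**1. Longest observable duration** (days divided by 30.4375). For the four long databases I count from 1 January 2017 to the lock in Table 3. This assumes that the 365 days of visibility are already met on that date. For VID, section 8.2 puts the data from the start of 2018 to the end of 2021, so with 365 days of prior visibility the first index date is about 1 January 2019.

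- VID: 1,096 days = 36.0 months (1,461 days = 48.0 if visibility before 2018 exists)
- IQVIA DA Germany: 2,463 days = 80.9
- FinOMOP-HILMO: 2,662 days = 87.5
- IPCI: 2,676 days = 87.9
- NLHR: 2,737 days = 89.9

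**2. Model (assumptions, not in the documents).** Time to discontinuation T is exponential with true median m, so λ = ln 2 / m. Initiations are spread evenly over a window W, so the time C from initiation to lock is uniform on (0, W). Lock is the only cause of cutting. The planned variable is then min(T, C), and

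- P(min(T, C) > t) = exp(−λt) × (1 − t/W); the raw median solves this for 0.5
- share of eras cut = (1 − exp(−λW)) / (λW)

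Example, VID with m = 24: λ = 0.0289. At t = 11.16, exp(−0.322) × (1 − 0.310) = 0.725 × 0.690 = 0.50. Share cut: λW = 1.040, and (1 − 0.353) / 1.040 = 0.62.

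**3. Results** (raw median in months, share of eras cut in brackets)

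| True median | Four long databases | VID, 36 months |
|---|---|---|
| 6 | 5.4 to 5.5 (10–11%) | 4.8 (24%) |
| 12 | 9.8 to 10.0 (19–21%) | 7.8 (42%) |
| 24 | 16.2 to 16.8 (36–39%) | 11.2 (62%) |

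If the VID window were 48 months, true medians of 12 and 24 would read 8.6 and 13.0. If uptake rises linearly instead of being even, the shortfall grows: a true 24 reads 12.4 to 13.1 in the long databases and 7.6 in VID.

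**4. Does the remedy work?** In simulation (400,000 patients per scenario, even uptake), Kaplan-Meier with lock as censoring returned 12.0 to 12.1 and 23.9 to 24.0 months in all five databases. The 90-day confirmation then matters. If an unconfirmed era is censored at its own end date, a true 24 reads 28.9 in a 36-month window and about 25 in the long ones, because real stops are turned into censorings. If every patient's censoring date is moved to 90 days before the end of observation, the same scenarios return 24.1 and 24.0.

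**The case against.** The strongest objections concern scope and remedy.

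- **Descriptive study.** No hypothesis or contrast is planned, and section 8.9 rules out meta-analysis. Observed time on drug within a database is a legitimate description and useful for feasibility. This stands, if the output is labelled that way; Table 1 promises time to discontinuation instead.
- **Size.** With a true median of 6 months the long databases lose only about half a month. VID, the worst case, has 600 of the 14,300 feasibility counts in section 8.7 (2500 + 700 + 7900 + 2600 + 600), or 4%. This stands: the size cannot be fixed from the documents.
- **Death.** A reader might infer from section 8.4 that death also biases durations short. It does not: death ends treatment, so that era is complete.
- **Newest JAKi.** A reader might infer that the most recently launched ingredient is worst affected. A shorter time on the market does mean more cutting, but the protocol dates only the approval of tofacitinib, so it does not show which ingredient that is or how long its window is.
- **IQVIA DA Germany.** This source holds 7,900 of 14,300 counts (55%), and by section 11 its observation ends at the last recorded interaction. A patient who stops and does not return is then censored close to the stop, which is informative and lengthens the Kaplan-Meier estimate. If a share q of stops is lost this way, an exponential median m becomes about m/(1 − q): for m = 12, 13.3, 15.0 and 17.1 months at q = 0.1, 0.2 and 0.3 (q is assumed). Above q of about 0.15 this error exceeds the 2.2 months (12 − 9.8) being corrected. This stands, and the fix has to deal with it.

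**Conclusion.** The point holds for data lock and loss to follow-up. The protocol fixes both the cutting rule and the raw quantiles, so this is not a detail left to an analysis plan, and the result will understate the quantity that Table 1 names. Two things are firm without any model: the direction, and that a shorter observable window makes the bias worse, which puts VID last among the databases. The monthly figures rest on exponential persistence, even uptake and cutting by lock alone. They range from negligible (short persistence, long window) to a halving or more (true 24 months in VID). The documents do not support calling death a source of the bias, ranking ingredients by how much they are affected, or quoting one size for it.

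**What to change.** In section 8.8.2, the abstract and Table 6:

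1. Estimate time to the end of the first era by Kaplan-Meier for each ingredient, indication and database, censoring at loss to follow-up and at data end.
2. Apply the 90-day confirmation by moving every patient's censoring date to 90 days before the end of observation. Do not censor unconfirmed eras at their own end date. Where observation ends in death, count the 90 days back from data end, so that the death itself is not lost.
3. Treat death as a terminal or competing event, and say which.
4. Report p25, median and p75, or *not reached*, with the number and share of eras cut. Keep the raw minimum, quantiles and maximum only if labelled as observed duration within the data window.
5. For IQVIA DA Germany, add a sensitivity analysis that counts the era end as discontinuation when the record ends well before data lock, with the interval fixed in advance.
6. Name truncation and informative censoring as limitations in section 11.

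No new data are needed. The cost is modest code beyond the standard package output, and some quantiles will not be reached: in the simulation, the VID p75 is not reached at true medians of 18 months or more. Patients who start within 90 days of the end of observation contribute no time to the estimate (about 8% in a 36-month window under even uptake, 90 / 1,096).

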8.9 Evidence synthesis

Results from analyses described in section 8.8 will be presented separately for each database and no metaanalysis of results will be conducted.

9. DATA MANAGEMENT

All databases will have been mapped to the OMOP common data model. This enables the use of standardised analytics and tools across the network since the structure of the data and the terminology system is harmonised. The OMOP CDM is developed and maintained by the Observational Health Data Sciences and Informatics (OHDSI) initiative and is described in detail on the wiki page of the CDM: https://ohdsi.github.io/CommonDataModel and in The Book of OHDSI: https://book.ohdsi.org.

This analytic code for this study will be written in R. Each data partner will execute the study code against their database containing patient-level data and will then return the results set which will only contain aggregated data. The results from each of the contributing data sites will then be combined in tables and figures for the study report.

[figure not shown]
10. QUALITY CONTROL

General database quality control

A number of open-source quality control mechanisms for the OMOP CDM have been developed (see Chapter 15 of The Book of OHDSI http://book.ohdsi.org/DataQuality.html). In particular, data partners have run the OHDSI Data Quality Dashboard tool (https://github.com/OHDSI/DataQualityDashboard). This tool provides numerous checks relating to the conformance, completeness and plausibility of the mapped data. Conformance focuses on checks that describe the compliance of the representation of data against internal or external formatting, relational, or computational definitions, completeness in the sense of data quality is solely focused on quantifying missingness, or the absence of data, while plausibility seeks to determine the believability or truthfulness of data values. Each of these categories has one or more subcategories and are evaluated in two contexts: validation and verification. Validation relates to how well data align with external benchmarks with expectations derived from known true standards, while verification relates to how well data conform to local knowledge, metadata descriptions, and system assumptions.

Study specific quality control

When defining specific drugs, conditions, and co-morbidities, a systematic search of possible codes for inclusion was previously identified using CodelistGenerator R package (https://github.com/darwin eu/CodelistGenerator). This software allows the user to define a search strategy and, using this will then query the vocabulary tables of the OMOP CDM to find potentially relevant codes. The codes returned will then be reviewed by two clinical epidemiologists to consider their relevance. In addition, the CohortDiagnostics R package (https://github.com/OHDSI/CohortDiagnostics) or a similar tool will be run to

assess the use of different codes across the databases contributing to the study and identify any codes potentially omitted in error. This will allow for a consideration of the validity of the study cohort of patients with the selected conditions, drugs, and co-morbidities in each of the databases and inform decisions around whether multiple definitions are required.

11. LIMITATIONS OF THE RESEARCH METHODS

The study will be informed by routinely collected health care data and so data quality issues must be considered. In particular, a recording of a prescription or dispensation does not mean that the patient actually took the drug. In addition, assumptions around the duration of drug use will be unavoidable.

The actual reason for prescription of the drug is not recorded in any of the databases. We will assess indication via a proxy based on pre-defined conditions recorded on the date of therapy initiation. Therefore, recording of potential indication may be incomplete. In addition, the completeness of recordings of co-morbidities used for patient characterisation may variate across databases.

In IQVIA DA Germany, the observation period of the patients in these databases is calculated based on the last visit, observation or interaction of the patient with the health care system. This methodology impacts the individuals considered "at risk" for the different medicines of interest of the study (i.e., the individuals included in the denominator populations) during the latest months of available data from the latest data lock, where healthy and/or non-frequent users of the health care system will not be considered active. Consequently, the denominators that will be used to calculate the incident use of drugs in the population may present an artefactual decrease whilst the incident users will remain. The presence of these artefacts will be considered when interpreting the results.

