The Integrated Primary Care Information (IPCI) database is a longitudinal observational database containing routinely collected data from computer-based patient records of a selected group of GPs throughout the Netherlands (N=723). IPCI was started in 1992 by the department of Medical Informatics of the Erasmus University Medical Center in Rotterdam with the objective to enable better post marketing surveillance of drugs. The current database includes patient records from 2006 on, when the size of the database started to increase significantly. In 2016, IPCI was certified as Regional Data Center. Since 2019 the data is also standardised to the Observational Medical Outcomes Partnership common data model (OMOP CDM), enabling collaborative research in a large network of databases within the Observational Health Data Sciences and Informatics (OHDSI) community. The primary goal of IPCI is to enable medical research. In addition, reports are generated to inform GPs and their organisations about the provided care. Contributing GPs are encouraged to use this information for their internal quality evaluation. The IPCI database is registered on the European Medicines Agency (EMA) ENCePP resources database (http://www.encepp.eu).

IQVIA Disease Analyzer Germany [IQVIA DA Germany] (Germany)

IQVIA Disease Analyzer (DA) Germany is a database of de-identified electronic medical records from specialised and general primary practices (GP) in Germany since 1992. This dataset encompasses approximately 3% of all outpatient practices within Germany, ensuring a substantial representation of the national healthcare landscape. The sampling methods used for practice selection, taking into account physician's demographics, specialty focus, community size category and federal state location, was instrumental in constructing a database that accurately mirrors the diverse spectrum of healthcare providers in the country. Consequently, data within IQVIA DA Germany database has been demonstrated to be representative of general and specialised practices throughout Germany.

P3-C1-001 Study	v Protocol
-----------------	------------

Version: V3.0

Dissemination level: Public

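### The partial-year 2023 incidence rate in IQVIA DA Germany is open to an upward bias that the protocol itself describes, yet the main series runs to the data lock with only a caution

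*Protocol*

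**What the plan says.** Section 11 (limitations) explains that the observation period in IQVIA DA Germany "is calculated based on the last visit, observation or interaction of the patient with the health care system". It places the consequence in the latest months before the data lock, "where healthy and/or non-frequent users of the health care system will not be considered active". It adds that the denominators "may present an artefactual decrease whilst the incident users will remain. The presence of these artefacts will be considered when interpreting the results". The second sentence of that quote is the only handling.

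The other sections make no exception for this source:

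- Section 8.3: "The study period starts from 1st January 2017 until the most recent data lock for each included database". Table 3 gives 30 September 2023 as the IQVIA DA lock, so 2023 is a nine-month year there.
- Section 8.4 ends each person's time at risk at the earliest of year end, end of data availability or first JAKi exposure.
- Section 8.8.2 defines the rate as new users "per 100,000 per-years of the population at risk of getting exposed during the period for each calendar year", with exact Poisson 95% intervals.
- Section 14 plots the annual rates for the class and for each ingredient.

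No section sets an earlier end date, a marker for the last year or an alternative denominator. Item 10.8 of the checklist in Appendix II, on sensitivity analyses, appears to be marked not applicable.

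**The concern.** The bias has a known direction. A person who is still registered but has not come in recently loses time at risk. A person who starts a JAKi has, by that prescription, a recorded contact and stays in the numerator. If the denominator shrinks in this way, the rate can only be pushed up.

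The bias also grows towards the lock, so it takes the form of a time trend. Sections 3 and 6 state the aim as incidence of new use over time. Someone looking at the German plot could not tell a rise in uptake from a loss of person-time, and a caution in the text gives no means of separating them.

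**Working it through.** The protocol states no incidence rate and no contact rate, so there is no planned figure to reproduce and the size cannot be derived from the documents. What follows is an illustration over an assumed range.

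**Inputs**

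- Lock: 30 September 2023 (Table 3). From 1 January 2023 that is L = 273/365.25 = 0.747 years.
- Observation ends at the last contact, and the numerator is kept (section 11).
- Assumption, not in the documents: non-users have random (Poisson) contacts at rate v per year, with v from 1 to 12, and otherwise remain in the practice.

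**Formulas**

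A person's time at t years before the lock is kept only if a contact falls between then and the lock, which has probability 1 − exp(−vt). Averaged over the window from a to b years before the lock:

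share kept = 1 − [exp(−va) − exp(−vb)] / [v(b − a)]

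Inflation of the rate = 1 / share kept. For 2023, a = 0 and b = 0.747; for 2022, a = 0.747 and b = 1.747.

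Example, v = 1 in 2023: 1 − (1 − exp(−0.747))/0.747 = 1 − 0.526/0.747 = 0.296, and 1/0.296 = 3.38.

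| Contacts per year, all non-users | Share kept 2023 | Inflation 2023 | Share kept 2022 | Inflation 2022 | Spurious ratio 2023/2022 |
|---|---|---|---|---|---|
| 1 | 0.296 | 3.38 | 0.701 | 1.43 | 2.37 |
| 2 | 0.481 | 2.08 | 0.903 | 1.11 | 1.88 |
| 4 | 0.682 | 1.47 | 0.988 | 1.01 | 1.45 |
| 6 | 0.780 | 1.28 | 0.998 | 1.00 | 1.28 |
| 12 | 0.889 | 1.13 | 1.000 | 1.00 | 1.13 |

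**Mixed populations**

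Each row applies one contact rate to the whole denominator. Section 11 speaks only of healthy or infrequent attenders, so two mixtures are more informative (both assumed):

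- 30% at one contact a year and the rest losing nothing: loss 0.30 × 0.704 = 0.211, inflation 1/0.789 = 1.27.
- 30% at v = 1, 40% at v = 4, 30% at v = 12: share kept 0.30 × 0.296 + 0.40 × 0.682 + 0.30 × 0.889 = 0.628, inflation 1.59 in 2023. The same mix keeps 0.905 in 2022 (inflation 1.10), a spurious 2023/2022 ratio of 1.44.

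**Would the confidence interval show it?**

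No. With an assumed 1,000 new users in a year, the exact Poisson limits are χ²(0.025; 2,000)/2 and χ²(0.975; 2,002)/2. Divided by 1,000 they are 0.939 and 1.064, or about −6% to +6%. The interval describes the count and takes the person-time as known.

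**The case against.** The strongest reply is that the protocol has not missed this. It names the cause, the part of the rate affected and the window, and it promises to take the artefact into account. The study is descriptive, tests no hypothesis, analyses each database separately and plans no meta-analysis, so the problem falls mainly on one announced point and enters no pooled estimate. A sensitivity cut-off might also sit in a statistical analysis plan that is not at hand.

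Much of that is fair: the issue is disclosed and contained. But disclosure leaves the plotted rate unchanged, and the protocol itself fixes both the end date (8.3) and the handling (11), so this is not simply a detail deferred.

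A second reply is that IQVIA DA has the largest feasibility count, 7,900 of 14,300 (2,500 + 700 + 7,900 + 2,600 + 600), and that recent data matter for newer indications. This has weight for Objective 2. Patient-level characterisation uses no person-time denominator, however, and need not be cut.

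Three stronger readings are tempting and are not supported:

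- *The 2023 point will show a rise.* The protocol says only that the denominator may fall, and the plotted direction also depends on the true trend, which is unknown.
- *The rate will be inflated two- or three-fold.* That needs the whole denominator to attend once or twice a year, and the documents give no contact rate.
- *The German level is too high because of sampling.* A reader might infer this by dividing Table 3 exposure counts by active subjects, or from the practice-based source ("This dataset encompasses approximately 3% of all outpatient practices within Germany"). Those quotients use ever-exposed persons and no person-time. The sources also differ in calendar span, specialist coverage and sex (VID holds women only). They cannot show that attender selection is the cause, and no comparison of levels between countries is planned.

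**Conclusion.** The point holds for the last, partial year of the IQVIA DA series. The mechanism and its upward direction come from section 11, and the plan still computes and plots the rate to 30 September 2023 with nothing beyond a promise of careful interpretation. The defect is a known, directional bias left without an analytic remedy; it is not an undisclosed one.

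The size is uncertain. Over the assumed 1 to 12 contacts a year for all non-users, the inflation runs from about 3.4-fold to 1.13-fold. In the two assumed mixtures, where infrequent attenders are a minority, it is 1.27-fold and 1.59-fold. It is above 1 in every case examined, but none of these factors is an estimate for this database. The change is a cheap improvement worth making. No conclusion is drawn about the level of the German rate or its comparison with other countries.

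**What to change.** In section 8.3, for Objective 1 only, end the main IQVIA DA Germany incidence series at 31 December 2022. In section 8.8.2, state that January to September 2023 will be calculated as a sensitivity result, shown apart from the main plot and flagged as a partial year whose denominator may be incomplete. Section 11 can then refer to this rule.

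The cost is one date cut-off and one label, and nine months of German incidence leave the main plot while remaining available in the sensitivity result. The cut-off need not remove all of the bias: in the illustration, 2022 inflation is 1.00 to 1.11 at two or more contacts a year and reaches 1.43 only if everyone attends once a year. That extreme case does not justify a further cut.
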